#### 9.6. Data Management

The database and data management plan will be generated to include the following as a minimum:

- Data Flow Plan;

- Case Report Form Completion Guidelines;
- Data Entry Methods and Guidelines;
- Data Validation Document;
- Data Handling Conventions.

A Data Clarification Form (DCF) process will be used for handling data discrepancies.

Data management and statistical analysis will be performed with SAS software.

#### **9.6.1. Case Report forms (CRFs)/Data Collection Tools (DCTs)/Electronic Data Record**

As used in this protocol, the term CRF should be understood to refer to either a paper form or an electronic data record or both, depending on the data collection method used in this study.

A CRF is required and should be completed for each included patient. The completed original CRF are the sole property of Pfizer and should not be made available in any form to third parties, except for authorized representatives of Pfizer or appropriate regulatory authorities, without written permission from Pfizer. The investigator shall ensure that the CRFs are securely stored at the study site in encrypted electronic form and will be password protected to prevent access by unauthorized third parties.

The investigator has ultimate responsibility for the collection and reporting of all clinical, safety, and laboratory data entered on the CRFs and any other data collection forms (source documents) and ensuring that they are accurate, authentic/original, attributable, complete, consistent, legible, timely (contemporaneous), enduring, and available when required. The CRFs must be signed by the investigator or by an authorized staff member to attest that the data contained on the CRFs are true. Any corrections to entries made in the CRFs or source documents must be dated, initialed, and explained (if necessary) and should not obscure the original entry.

In most cases the source documents are the hospital or the physician's chart. In these cases, data collected on the CRFs must match those charts.

In some cases, the CRF may also serve as the source document. In these cases, a document should be available at the investigator site and at Pfizer that clearly identifies those data that will be recorded on the CRF, and for which the CRF will stand as the source document.

#### **9.6.2. Record Retention**

To enable evaluations and/or inspections/audits from regulatory authorities or Pfizer, the investigator agrees to keep records, including the identity of all participating patients (sufficient information to link records, eg, CRFs and hospital records), all original signed informed consent documents, copies of all CRFs, safety reporting forms, source documents, detailed records of treatment disposition, and adequate documentation of relevant

correspondence (eg, letters, meeting minutes, and telephone call reports). The records should be retained by the investigator according to local regulations or as specified in the clinical study agreement (CSA), whichever is longer. The investigator must ensure that the records continue to be stored securely for so long as they are retained.

If the investigator becomes unable for any reason to continue to retain study records for the required period (eg, retirement, relocation), Pfizer should be prospectively notified. The study records must be transferred to a designee acceptable to Pfizer, such as another investigator, another institution, or to an independent third party arranged by Pfizer.

Investigator records must be kept for a minimum of 15 years after completion or discontinuation of the study or for longer if required by applicable local regulations.

The investigator must obtain Pfizer's written permission before disposing of any records, even if retention requirements have been met.

## **9.7. Data analysis**

Detailed methodology for summary and statistical analyses of data collected in this study will be documented in a Statistical Analysis Plan (SAP), which will be dated, filed and maintained by the sponsor. The SAP may modify the plans outlined in the protocol; any major modifications of primary endpoint definitions or their analyses would be reflected in a protocol amendment.

- Descriptive analysis will be performed for all the variables;
- Analysis will be stratified by age [50 to  $\leq 55$  ; 55 to  $\leq 60$ ; 60 to  $\leq 65$ ; 65 to  $\leq 70$ ; 70 to  $\leq 75$ ; 75 to  $\leq 80$ ; >80 years old], gender and cardiac symptomatology at entry;
- Patients with a final diagnosis of ATTR-CM will be compared with the patients who do not have a final diagnosis of ATTR-CM in order to highlight possible diagnostic red flags;
- Factors associated to ATTR amyloidosis will be identified by univariate and multivariate logistic regression. A significance level of 10% and 5% will be used for the univariate and multivariate analyses, respectively.

An interim analysis of the data collected will be performed for all the variables as soon as 75 patients will be selected with a scintigraphy grade 1, 2 or 3 and with completed e-CRF.

## **9.8. Quality Control**

### **9.8.1. Investigational Site Set Up**

Appropriate training relevant to the study will be given to investigational staff. Any new information relevant to the performance of this Study will be forwarded to the staff during the study.

### **9.8.2. Investigational Site Monitoring**

Regular contacts with the sites will be planned to provide information and support to the investigator(s) and verify that study sites procedures are compliant with the protocol and that data are being accurately recorded in the CRFs.

Additional monitoring tasks will be described in a monitoring plan according to Pfizer SOP; monitoring visit at investigators sites will ensure that:

- information letters have been given to the patients and consents have been signed;
- study is conducted according to the protocol;
- data reported on case report forms is compliant with source documents;
- study documents are correctly archived in accordance with the investigator's study file.

### **9.8.3. Study Coordination**

Regular progress reports presenting key indicators at a National and International level will be regularly prepared and forwarded to the study coordinating team. Based on these status reports, different actions will be decided by the study coordinating team to ensure a satisfactory progress and an appropriate quality of data.

Different signals (Protocol deviations as identified by monitoring) will be used as potential identification of low protocol compliance by investigators.

### **9.8.4. Quality and Accuracy of Records**

The investigator will have the responsibility for collecting and reporting of all clinical, safety and laboratory data entered in the e-CRFs and/or any other data collection forms (source documents) and ensuring that they are accurate, authentic/original, attributable, complete, consistent, legible, timely (contemporaneous), enduring and available when required.

To enable evaluations and/or audits from regulatory authorities or Pfizer, the investigator agrees to keep records, including the identity of all participating subjects (sufficient information to link records, eg, CRFs and hospital records), all original signed informed consent forms, copies of all CRFs, serious adverse event forms, source documents, and detailed records of treatment disposition, and adequate documentation of relevant correspondence (eg, letters, meeting minutes, telephone call reports).

### **9.8.5. Storage of Record**

The records should be retained by the investigator according to local regulations, and/ or as specified in the Clinical Study Agreement.

## **9.9. Limitations of the Research Methods**

### **9.9.1. Investigational Site Selection**

The voluntary participation of physicians constitutes a selection bias observed for this type of study. Investigational sites will be recruited within a list of the country's centers, representative in terms of size, care management system and practices.

### **9.9.2. Patient Selection**

This constitutes another potential selection bias classically associated with studies. Voluntary or involuntary selection of patients in a study by investigators is inevitable, but this bias can be limited by systematic attempts to enroll patients in the study.

### **9.9.3. Patients Lost to Follow-up**

The pragmatic nature of this study (which involves non-intervention on usual patient management practices) may increase the number of patients lost to follow-up after the scintigraphy results reported.

Monitoring on site, remote monitoring and warnings implemented in the e-CRF should minimize this.

### **9.9.4. Measurement Biases**

The assessment of the primary endpoint is based on the bone scintigraphy reading, which implies an evaluator-dependent variability and may create a bias.

In order to measure this bias scintigraphy reviews by external evaluators have been planned. Digitalized images will be reviewed by two external evaluators to analyze level of concordance/discrepancies among different specialists as part of a secondary objective for the study.

Secondary endpoints are based on laboratory analyses and may constitute a bias as each site has their own process, units and norms. They are also based on symptom assessment that may differ from an investigator to another and may constitute a bias.

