### **9.2.2. Inclusion Criteria**

The study will enroll patients according to the eligibility criteria in participating countries. The recruiting centers will be representative of each country involved in terms of care management systems, of size and of practices (at least when performing feasibility).

To ensure equitable recruitment, each site will be limited to a 100 screened patient maximum.

All patients who met the inclusion and exclusion criteria will be invited to participate in the study.

An informed consent document, will be signed by each patient before any data collection (Appendix 1).

If a patient isn't included in the study for any reason, the non-inclusion register has to be completed (Appendix 2).

The enrollment visit will be performed at the time of inclusion, after the patients' acceptance of enrollment in the study and Informed Consent Document signature.

Data will come from medical records and will be collected in routine clinical practice. The enrollment visit will comprise a first section on patients' eligibility for every patient and a second section on the patient information, family history and clinical evaluation at the inclusion.

After the patient undergoes a Bone Scintigraphy and/or SPECT as part of standard of care (Annex 3) the images will be evaluated by the nuclear medicine specialist of the investigational center.

Scans will be defined at each site according to the internationally accepted grading:

*Grade 0 = absent cardiac uptake*

*Grade 1 = mild uptake less than bone*

*Grade 2 = moderate uptake equal to bone*

*Grade 3 = high uptake greater than bone*

For all patients with cardiac fixation at scintigraphy and/or SPECT the following data will be collected and incorporated in the CRF if available:

- Answers from questions regarding ATTR amyloidosis red flags
- Results from clinical laboratory tests and genotyping.

The patient will finish the study after this visit.

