### **9.2.3. Centralized Review of Bone Scintigraphy (for all patients)**

In this study, all the scintigraphy/SPECT tests will be additionally reviewed by two external evaluators.

The objective of this evaluation will be to assess the level of discrepancy in the evaluation of the scintigraphy/SPECT images by different evaluators

All the scintigraphy/SPECT tests will be uploaded in a dedicated database via the study web site.

Two experts from the scientific committee members will connect to the study web site with personalized connection access. They'll review the scintigraphies/SPECT and enter their evaluation.

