### 6.3 OTHER ENDPOINTS

#### Primary endpoint

Patients with cardiac fixation at the radionuclide bone scintigraphy and/or SPECT performed with 99mTc-DPD or 99mTc-PYP or 99mTc-HMDP will be defined as patients with a cardiac retention of grade 1, grade 2 or grade 3.

Patients without cardiac fixation at the radionuclide bone scintigraphy performed and/or SPECT with 99mTc-DPD or 99mTc-PYP or 99mTc-HMDP will be defined as patients with a cardiac retention of grade 0.

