### 7. Scintigraphy discrepancies analysis

Discrepancy in the evaluation of the scintigraphy and/or SPECT images by different evaluators will be analyzed as follow:

- Between site and 1st evaluator:

Cross tabulation between the two evaluators

Scintigraphy or SPECT images	Site evaluation				
	Grade	0	1	2	3
1 st external evaluator	0				
	1				
	2				
	3				

PFIZER CONFIDENTIAL

All percentages of discrepancies will be provided.

A weighted Kappa coefficient (measure of interrater agreement) will be provided with 95% confidence limits and exact test for the kappa coefficient.

- Between 1st and 2nd evaluators (in case there is a discrepancy between site evaluation and 1st external evaluator), same analyses will be performed.
- A listing of all individual patients will be provided for all discrepancies (site and the 2 external evaluations).

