## 8. Sensitivity analyses

### 1) Impact of protocol amendment 2 - Use of SPECT

The prevalence of patients with cardiac fixation at the radionuclide bone scintigraphy and/or Single Photon Emission Computed Tomography (SPECT) performed with 99mTc-DPD or 99mTc-PYP or 99mTc-HMDP\* among patients with (left ventricular hypertrophy) LVH from undiagnosed etiology will be calculated in patients included before protocol amendment and in patients included after protocol amendment (Amendment 2 – Date: 11-Feb-2020). The percentage and its 95% CI will be provided.

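### Reader disagreement is tabulated and summarised by kappa, but the primary prevalence is never re-estimated on the external or consensus reading

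*Protocol*

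**What the plan says.** Grades are assigned locally. Protocol 9.2.2 states: "Scans will be defined at each site according to the internationally accepted grading". SAP 2.1 repeats this. SAP 6.3 defines the primary endpoint by grade, so that positive patients "will be defined as patients with a cardiac retention of grade 1, grade 2 or grade 3", but it does not name the reader whose grade counts. FAS2 and FAS3 (SAP 5.1) are also defined by grade.

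Protocol 9.9.4 acknowledges the dependence on the evaluator: "The assessment of the primary endpoint is based on the bone scintigraphy reading, which implies an evaluator-dependent variability and may create a bias". It continues: "In order to measure this bias scintigraphy reviews by external evaluators have been planned". Under Protocol 9.2.3, "all the scintigraphy/SPECT tests will be additionally reviewed by two external evaluators".

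SAP 8.2, Other analyses, item 7, is run on FAS1. It plans:

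- a 4×4 table of site grade by first external evaluator's grade;
- all discrepancy percentages;
- agreement statistics: "A weighted Kappa coefficient (measure of interrater agreement) will be provided with 95% confidence limits";
- the same outputs for first versus second evaluator where site and first evaluator disagree;
- a listing of discrepant patients with all three grades.

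Item 8 holds two sensitivity analyses. One concerns SPECT and the other the central laboratory. In both, the prevalence "will be calculated in patients included before protocol amendment and in patients included after protocol amendment". Neither compares readers. The shell of Table 15.2.1 has a single prevalence.

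**The concern.** The protocol's reason for the re-read is possible bias in the primary endpoint. The SAP's summary statistic for it is an agreement coefficient, which answers a different question. Kappa says how often readers agree beyond chance. It does not say whether the disagreements cancel or all push the prevalence one way.

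Most scans are expected to be negative, so a small one-way tendency to call faint uptake grade 1 could move the prevalence by as much as its stated precision while kappa stays high. Movement across the grade 1/2 boundary matters as well. SAP 6.3 treats grade 1 as undetermined, whereas grade 2 or 3 without monoclonal protein abnormalities counts as ATTR amyloidosis. The report could therefore put a high kappa beside a single site-based prevalence and leave the reader to work out how far the two readings differ on the main result.

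**Working it through.** **1. The plan's own precision.** Protocol 9.5 assumes 10% prevalence, N = 1500 and a two-sided 95% interval. The half-width is 1.96 × √(0.10 × 0.90 / 1500) = 1.52 points, which reproduces the stated ±1.5. The Wilson interval for 150/1500 is 8.6% to 11.6%. The Abstract's milestones also allow data collection to end at 1000 patients, where the half-width is 1.96 × √(0.09/1000) = 1.86 points. Protocol 9.5 states the 10% for ATTR-CM. It is used here as a stand-in for any uptake (grade 1 to 3), for which no figure is given.

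**2. Shift and kappa under assumed error rates.** The documents give no site-versus-expert error rates. Take the external reading as reference, with 10% positive, site sensitivity Se and specificity Sp:

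- observed prevalence q = 0.10·Se + 0.90·(1 − Sp)
- observed agreement po = 0.10·Se + 0.90·Sp
- chance agreement pe = 0.10·q + 0.90·(1 − q)
- binary kappa = (po − pe)/(1 − pe)

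| Se / Sp | q | Shift (points) | po | pe | Kappa |
|---|---|---|---|---|---|
| 90% / 99% | 0.090 + 0.009 = 9.9% | −0.1 | 0.981 | 0.8208 | 0.89 |
| 99% / 99% | 0.099 + 0.009 = 10.8% | +0.8 | 0.990 | 0.8136 | 0.95 |
| 90% / 98% | 0.090 + 0.018 = 10.8% | +0.8 | 0.972 | 0.8136 | 0.85 |
| 95% / 98% | 0.095 + 0.018 = 11.3% | +1.3 | 0.977 | 0.8096 | 0.88 |
| 99% / 98% | 0.099 + 0.018 = 11.7% | +1.7 | 0.981 | 0.8064 | 0.90 |
| 99% / 97% | 0.099 + 0.027 = 12.6% | +2.6 | 0.972 | 0.7992 | 0.86 |

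Four of the six cases stay inside ±1.5 points and two exceed it. At N = 1000 only the last exceeds the half-width. Kappa does not order the shifts: 0.89 goes with −0.1 and 0.90 with +1.7.

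**3. The same on four grades.** The SAP specifies a weighted kappa without naming the weights, so linear weights are assumed. Take N = 1500 and 150 site positives (40 grade 1, 50 grade 2, 60 grade 3). In each table 40 scans (2.7%) are discrepant, all between grades 0 and 1. Kappa = 1 − D/E, where D is the observed and E the chance-expected weighted disagreement. D = 40/(3 × 1500) = 0.0089 in all three tables.

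| Direction of the 40 | E | Weighted kappa | External prevalence (Wilson 95% CI) |
|---|---|---|---|
| 20 each way | 0.1309 | 0.932 | 150/1500 = 10.0% (8.6 to 11.6) |
| All site 1, external 0 | 0.1238 | 0.928 | 110/1500 = 7.3% (6.1 to 8.8) |
| All site 0, external 1 | 0.1380 | 0.936 | 190/1500 = 12.7% (11.1 to 14.5) |

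A net 23 scans moving one way (23/1500 = 1.53 points) equals the whole stated half-width.

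**4. Why the paired difference is needed.** In the second row, the site interval (8.6 to 11.6) and the external interval (6.1 to 8.8) overlap. The paired difference is 40/1500 = 2.67 points, with standard error √(40 − 40²/1500)/1500 = 0.42 points and a Wald 95% CI of about 1.85 to 3.48. Side-by-side intervals would understate how clearly the two readings differ.

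**The case against.** A reader might infer that the bias is never measured. The documents do not support that. If the first evaluator reads all of FAS1, as planned, the margins of the 4×4 table give the prevalence by site and by that evaluator, and the off-diagonal cells show the direction of disagreement. With the discrepancy listing, a median-based count could also be assembled by hand.

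A reader might also infer that the SAP breaks a protocol promise. It does not. Protocol 9.9.4 goes on to describe the review as an analysis of concordance and discrepancy under a secondary objective, and neither document commits to re-estimating the prevalence.

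Nor do the documents show that the primary prevalence is inflated. They give no error rates, and the assumed ranges above include shifts near zero.

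Finally, the study is descriptive, with no inferential hypothesis (SAP 4.1), and reader dependence is disclosed as a limitation.

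All of this stands, and it limits the point to a reporting gap. A margin worked out by hand has no interval, no paired difference, no consensus grade, no recount of FAS2 and FAS3, and no place beside the primary result unless someone decides to put it there after seeing it.

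**Conclusion.** The point holds as a gap in the planned reporting that is cheap to close. Reader disagreement is measured, but its effect on the primary prevalence is not a planned estimate, and kappa cannot stand in for one. Under the assumed error rates the shift runs from −0.1 to +2.6 points against ±1.5. With 40 discrepant scans in 1500, weighted kappa of 0.93 to 0.94 is compatible with an external prevalence of 7.3%, 10.0% or 12.7%.

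These sizes rest on the assumed 10% prevalence, assumed error rates and discrepancy patterns, linear weights, and the external reading as reference. They show what kappa can conceal. They do not predict what this study will find.

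**What to change.** Add a third sensitivity analysis to SAP 8.2, Other analyses, item 8. Repeat Table 15.2.1 and the FAS2 and FAS3 counts on:

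- (a) the first external evaluator's grade;
- (b) the median of the site, first-evaluator and second-evaluator grades. Where site and first evaluator agree, the median is their common grade, so (b) works whether the second evaluator reads every scan (Protocol 9.2.3) or contributes only on discrepant ones (SAP item 7).

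Give each prevalence with its Wilson 95% CI, plus the paired difference from the site-based prevalence with its own 95% CI, and the number of FAS1 patients lacking an external grade. Both versions are needed because the median gives the site one of three votes and so is not an independent expert estimate. State in SAP 6.3 that the site grade defines the primary endpoint.

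The cost is one SAP paragraph and one table, with no new reads. There is one limit. Laboratory and genotype results are collected only after a positive site reading (Protocol 9.2.2, 9.2.5.1 and 9.4), so patients positive only on external reading cannot be placed in FAS3.1 or FAS3.2. Report them as unclassified; ATTR status is then recomputed only in part.

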## **9.10. Other Aspects**

If a physician agrees to participate in this study, a written agreement will be concluded with this physician containing the amount of allowance paid for the documentation of one subject. The agreed allowance is paid for the workload involved in the documentation of the treatment on the specific e-CRF.

Since no other examinations will be performed than the usual clinical examinations and laboratory tests, the medical services provided and the drugs will be reimbursed by the health insurer.

## **10. PROTECTION OF HUMAN SUBJECTS**

### **10.1. Patient Information**

All parties will comply with all applicable laws, including laws regarding the implementation of organizational and technical measures to ensure protection of patient personal data. Such measures will include omitting patient names or other directly identifiable data in any reports, publications, or other disclosures, except where required by applicable laws.

The personal data will be stored at the study site in encrypted electronic form and will be password protected to ensure that only authorized study staffs have access. The study site will implement appropriate technical and organizational measures to ensure that the personal data can be recovered in the event of disaster. In the event of a potential personal data breach, the study site shall be responsible for determining whether a personal data breach has in fact occurred and, if so, providing breach notifications as required by law.

To protect the rights and freedoms of natural persons with regard to the processing of personal data, when study data are compiled for transfer to Pfizer and other authorized parties, patient names will be removed and will be replaced by a single, specific, numerical code, based on a numbering system defined by Pfizer. All other identifiable data transferred to Pfizer or other authorized parties will be identified by this single, patient-specific code. The investigator site will maintain a confidential list of patients who participated in the study, linking each patient's numerical code to his or her actual identity. In case of data transfer, Pfizer will maintain high standards of confidentiality and protection of patients' personal data consistent with the Clinical Study Agreement and applicable privacy laws.

